## IRB Protocol

### 1. Title:

Revitalize Cognition: A Proof of Concept Study with Transcranial Near Infrared Stimulation in Cognitively Normal Older Adults, those with Mild Cognitive Impairment or Parkinson Disease

### 3. Abstract

Cognitive decline and transition to dementia, particularly Alzheimer's disease, is one of the most prominent public health concerns of the 21st century. Over the past decade, progress has been made in identifying subtypes of dementia, preclinical biomarkers and associated risk factors, along with strides in understanding the role of various suspected pathophysiologic mechanisms. Even so, there is a dearth of clinically meaningful treatment options at this point in time for individuals who are at increased risk for transitioning to dementia, particularly those with the amnestic variant of mild cognitive impairment (aMCI). While waiting for causative cures and preventive approaches, we are faced with the task of identifying modifying therapies that might alter the course or slow down the transition from aMCI to Alzheimer's dementia. Similar concerns face other neurodegenerative disorders (e.g., Parkinson disease) regarding transitions from mild cognitive impairment to dementia.

The proposed study hopes to contribute to this mission by testing the viability of a different type of intervention, one involving transcranial delivery of near-infrared (NIR) wavelengths (808-904nm). Near-infrared stimulation is safe, non-invasive and appears to improve mitochondrial function by promoting increased production of intracellular ATP and possibly improved blood flow. Perhaps most compelling are recent findings of reduced beta-amyloid and neurofibrillary tangles in transgenic Alzheimer's mouse models after exposure to real vs sham transcranial NIR stimulation. Similar observations have emerged in mouse models of

Parkinson disease. Preliminary human studies involving TBI, stroke, and young adult populations have also been promising in terms of positive effects of NIR on cognition.

The overall goal of the present study is to learn whether this unconventional NIR stimulation approach has potential for improving cognition in older adults. To do so, we will conduct a randomized sham controlled pilot trial. The intervention will involve six sessions, over a 2-week period in which real or sham stimulation is transcranially applied using a delivery system that has been FDA-approved as a nonsignificant risk since 2003. We hope to learn whether NIR stimulation, relative to sham, has positive effects on: a) novel tasks of memory that are sensitive to hippocampal function and amyloid burden; b) executive tasks from the NIH Examiner, and c) emotion measures, including those from the emotion module of the NIH Toolbox. An exploratory neuroimaging aim will examine pre-post intervention changes in resting state connectivity and MRS phosphorus ATP in a subset of participants who are eligible to undergo magnetic resonance imaging. A subgroup of participants with Parkinson disease will participate and will undergo similar procedures in addition to motor testing. If findings from this study are positive, this may set the stage for more finely tuned trials examining various dosage parameters. Transcranial NIR stimulation is an understudied intervention that could potentially represent a strategy for enhancing thinking and memory in older adults and those with mild cognitive impairment or pre-Alzheimer's disease.

#### **4. Background**

The proposed project represents a novel, relatively low cost, low risk, though potentially high impact approach for a cognitive/ mood intervention in older adults. It involves transcranial delivery of near infrared (NIR) light via light emitting diodes. Before describing the study design, we will briefly describe the background and rationale for this unconventional approach

By history, current nonsurgical device approaches to brain stimulation primarily involve magnetic (rTMS, TMS, deep TMS) or electrical stimulation approaches (transcranial direct current stimulation (tDCS) which alter synaptic firing rates and neuronal membrane potentials.

In contrast, a very different type of brain stimulation approach involves near infrared light (NIR). Application of light in red (630-700nm) and near-infrared wavelengths (808-904nm) appears to improve mitochondrial function by promoting increased production of intracellular ATP, which is important for cellular metabolism, respiration and oxygenation. It increases blood flow and upregulates the expression of neuroprotective genes. Specifically, it targets the cytochrome oxidase c integral membrane protein of the mitochondrial membrane (electron transport chain) and leads to: a) increased intracellular levels of ATP (Mochizuka-Oda et al., 2002, Wong-Riley et al., 2005, Oron et al., 2007), b) increased expression of genes supporting cell proliferation and mitochondrial energy metabolism (Zhang et al., 2003), and c) decreased genes for pro-inflammatory proteins such as interleukin-1, interleukin10, and cytokine receptors (Whelan et al., 2003). Additionally, near infrared light may increase blood flow (Chung et al., 2012; Nawashiro et al., 2012) and up-regulate antioxidant genes (Chen et al., 2009). Thus, rather than directly modulating neural networks per se, application of NIR appears to create a supportive environment for optimal neuronal functioning. Its influence on neural connectivity is thus indirect rather than direct.

Recent animal and human studies have provided tentative support for positive benefits of this NIR approach in terms of "brain and cognitive function". Animal studies have included reports of reduced beta-amyloid load and neurofibrillary tangles in transgenic mice (APP/PS1 and

K3Tau) expected to develop Alzheimer's disease after exposure to real vs sham transcranial NIR stimulation (Purushothuman et al., 2014, 2015). Others, using mouse and macaque models of Parkinson disease, have found that leads with NIR- attached diodes implanted into the ventricles protected dopaminergic neurons in the substantia nigra from MPTP-induced degeneration and also preserved locomotor activity (Moro et al, 2013, 2014). Still others have reported that NIR light stimulation attenuates post-stroke deficits in rabbits (Lapchak et al., 2007, 2010) and increases cortical metabolism and memory retention in healthy rats (Rojas et al., 2012).

In human studies, near infrared stimulation has been applied via diodes directly to the scalp and is thought to penetrate 1-3 centimeters deep, with approximately 2-3% of the light reaching the cortex (Wan, 1981; Naeser et al., 2014). Stimulation is carried out using FDA-cleared devices that are deemed safe, painless and non-invasive. Studies of NIR stimulation typically use lasers, light emitting diodes (LEDs), or superluminous diodes (i.e., an LED variant that produces stronger light). The FDA originally approved the technology in 2003 as a nonsignificant risk device and the application of this technology in humans has been shown to be safe and effective (Rojas & Gonzalez-Lima, 2013).

In humans, positive effects with NIR stimulation have been observed in individuals with chronic aphasia due to focal stroke (Naeser et al., 2012, 2013), in individuals with traumatic brain injury who underwent a six week intervention study (Naeser et al., 2014), and in young healthy adults (Barrett et al., 2013). The latter study was 'sham controlled' and with young adults undergoing only one session of NIR stimulation, resulting in changes on tasks of executive functioning and processing speed. Patients with TBI showed improvement on tasks of executive function and recent memory, with relatively large effect sizes ranging from changes on the order of 1-2 standard deviations. At least one neuroimaging study has reported pre-post changes in resting state functional connectivity MRI following application of real vs. sham NIR.

**Summary:** While findings from both animal and human studies are promising, it remains unclear whether such a novel, unconventional approach might be viable for enhancing in older adults, including those at risk for developing Alzheimer's disease. More carefully controlled studies are clearly needed. Currently, we have available NIR instrumentation (MedX, FDA cleared as nonsignificant risk device) that was obtained from a McKnight Brain Institute shared instrumentation grant. The current proposal intends to use this system to pilot a randomized sham-controlled study in cognitively normal older adults, those with mild cognitive impairment (amnestic, nonamnestic), and nondemented individuals with Parkinson disease.

## 5. Specific Aims

[figure not shown]
1. **Aim 1: To test the hypothesis that NIR stimulation will result in greater pre-post intervention improvement on tasks of executive function (co-primary outcome) and recent memory (co-primary outcome).** Executive function will be tested using individual and composite scores from the NIH Examiner, a battery of executive function tests (Kramer et al., 2014) and an experimental Stroop task. The co-primary outcome includes a novel task of recent memory that is sensitive to hippocampal function and amyloid load, the Spatial Navigation Task which is also known as ARENA (Thomas et al., 2001; Laczo et al., 2011). Additional executive and memory measures will serve as secondary cognitive outcomes..

2. **Aim 2:** *To test the hypothesis that NIR stimulation will result in greater pre-post intervention improvement, relative to sham, on measures of mood, negative affect and wellbeing.* This will be tested using indices from the Emotion module of the NIH Toolbox (Salsman et al., 2013) and traditional measures of depression, anxiety, and apathy.
3. **Aim 3:** (exploratory): *To learn whether there are intervention-related changes in resting state functional connectivity and/or MRS-based markers of ATP function.* This will be sampled in a subgroup of participants who undergo structural and functional MRI before and after intervention, either NIR treatment or sham conditions.
4. **Aim 4:** (Parkinson specific): **To learn whether there are intervention-related changes in motor skills.** This will be tested using measures of fine motor speed and dexterity (Grooved Pegboard), gait and balance, and clinical measures of Parkinson disease severity.

## 6. Research Plan

### 6.1 Design Overview

This is a pilot study of the efficacy of NIR stimulation for enhancing cognition and mood in older adults including those who are cognitively normal, those with mild cognitive impairment (amnestic and nonamnestic), and individuals with Parkinson disease. The overall hypothesis, drawn from previous literature, is that exposure to NIR stimulation will have positive effects on brain health and will result in better cognitive and mood performance. We propose to conduct a blinded parallel group sham controlled pilot trial, with half the participants in each group randomized to the real NIR treatment and half to the sham treatment condition. The two conditions are identical in all respects except that no near-infrared light stimulation will occur during the sham condition. The participants will consist of older adults recruited from the community, including The Village, and from UF and other clinics. The study will take place at the UF-VITAL lab located on The Village campus or in the Cognitive Neuroscience Laboratory at the Fixel Center for Neurologic Disease. The study design is shown below:

## 6.2 Participants

Participants will include individuals, age 62 years and older, who are independently living and willing to undergo a two-week intervention program. Our study groups will consist of the following: 70 cognitively normal individuals (N= 35/group), 20 individuals with amnestic MCI (N=10/group), 20 individuals with nonamnestic MCI (N=10/group), and 40 nondemented individuals with Parkinson disease (N=20/group). Based on our previous intervention studies with older adults, we anticipate a 20% attrition rate and up to 50 screen failures. To account for screening failures and study attrition, we anticipate consenting 206 individuals.

**Informed Consent:** Informed consent will be obtained according to university and federal guidelines. The informed consent process may begin with the initial telephone screening call, when a prospective participant is contacted or calls to find out more information about the study (See Telephone Script). After that first phone contact, the participant will be sent a copy of the Informed Consent via hardmail or via email if they are interested, and/or scheduled for an appointment in the VITAL laboratory or at the Fixel Center for Neurologic Diseases to discuss the study in more detail and in person.

Other potential participants, particularly those seen during the clinics of the PI or co-investigators, will be directly asked about their interest in this study and will be provided a copy of the informed consent to review.

During the first study visit, the project will be explained in more detail to the potential participant by the study coordinator or approved staff and the Informed Consent will be reviewed. Participants will be informed that this is a randomized trial and that there is 50% likelihood they may receive the sham intervention. The participant will be given the opportunity to ask questions. No study interventions will begin until the Informed Consent

(ICF) paperwork is signed. Participant will be given a signed copy of the ICF paperwork, and a copy will be kept on file with the Principal Investigator.

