## 6.6 Pre and Post-Intervention Measures

Participants who meet study criteria and who remain interested in participating in the 2 week intervention will be randomized to treatment or sham groups and undergo a baseline/ pre-intervention testing. The pre-intervention measures will be administered by a trained psychometrist or research assistant who will be blinded to group assignment (sham, real NIR stimulation).

The pre-intervention testing will take approximately 3 – 3.5 hours, and will consist of measures of executive function, recent memory, and mood. These same measures will be given after the two-week intervention has completed.

Individuals with Parkinson disease will complete the pre and post intervention visits when they are “off” their typical dopaminergic medications. This is identical to what Parkinson patients are asked to do as part of standard clinical care when seen at the UF Movement Disorders Clinic. To do so, the Parkinson patients will refrain from taking their parkinsonian medications overnight, with no dopa medication after 10:00 PM the night before. The theoretical rationale for evaluating patients when off dopamine medication is to obtain an index of the true status of their disease state.. The remainder of the protocol (i.e., screening, intervention) will be completed when participants are on their normal medications. When tested ‘off medication’, patients may experience increased slowness, tremors and stability. Because of this, they will be closely monitored and provided a wheel chair. If they become too uncomfortable they can take their medication and will be withdrawn from the study.

In previous IRB- approved studies, we have tested Parkinson patients off medication while they completed an array of cognitive, EEG, and other tasks. We have found that the tolerability was quite good and no participants dropped out of the study for the medication issue. In the current study, we are implementing testing ‘off dopa’ medications at the recommendation of the Parkinson Foundation.

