## 7.2. Randomization and Statistical Methods

**7.2.a. Randomization.** Participants in the Cognitively Normal, the MCI, and Parkinson groups will be independently assigned to Sham and Treatment groups on a 1:1 ratio. For the Cognitively Normal group, we anticipate an N of 35 in each treatment group. For each MCI group, we anticipate an N of 10 per treatment group. For the PD group, we anticipate an N of 20 per treatment group. Randomization will be stratified according to age and MoCA/MMSE scores so as to prevent different average ages or cognitive status scores between the treatment groups. Treatment assignment will be pseudorandomized in order to have comparable distributions of age and cognitive screening scores across Sham and Treatment interventions. Procedures will be followed so that group assignments are not available to individuals administering and scoring baseline/pre-intervention and post-intervention cognitive/mood data.

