### **9. Study Time Line Schedule of Activities**

The Schedule of Participant Activities for this study is as follows:

- **Call #1**- Telephone Prescreening to review the study details, and inclusion/exclusions.
- **Informed Consent Process and Screening Visit**- Informed Consent Process begins with the participant per UF, state and federal guidelines. Once the participant has signed the informed consent, complete medical history, inclusion/exclusion criteria, concomitant medications, and cognitive and mood questionnaires will be administered (listed in section C). If participant formally meets study criteria, then he or she is invited to participate in the intervention phase of the study consisting of baseline, NIR stimulation, and post-baseline testing.
- **Baseline Visit** - This assessment involves a series of computer based measures and other questionnaires. This visit may take approximately 3-3.5 hours. If participants undergo MRI, this will take an additional 1.5 hours.
- **NIR Invention (six in lab sessions over two weeks)** - After completing baseline testing, participants will undergo a series of six interventions in the lab over a period of two weeks. The six treatment visits will be scheduled at the baseline visit to ensure availability of the participant. The treatment will be applied over the head and is detailed in section C. During each treatment visit, participants will fill out mood questionnaires such the POMS. .
- **Post-Treatment Visit**- Following the final day of stimulation, the participant will be scheduled for a post-testing assessment of cognitive and emotional function identical to the baseline visit. Participants will also fill out other questionnaires such as the adverse events and placebo control questionnaires.

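### The 206 planned consents cannot cover both 50 screen failures and 20% attrition for study groups that total 150

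*Protocol*

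**What the plan says.** Section 6.2 plans 70 cognitively normal participants (35 per arm), 20 with amnestic MCI (10 per arm), 20 with nonamnestic MCI (10 per arm) and 40 with Parkinson disease (20 per arm). It gives the allowances as "we anticipate a 20% attrition rate and up to 50 screen failures" and draws the enrolment figure from them: "To account for screening failures and study attrition, we anticipate consenting 206 individuals".

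Two other sections bear on what the group sizes mean. Section 6.1 describes "half the participants in each group randomized to the real NIR treatment". Section 7.2.a says that the groups "will be independently assigned to Sham and Treatment groups on a 1:1 ratio" and repeats the sizes in that setting: "we anticipate an N of 35 in each treatment group", and "For each MCI group, we anticipate an N of 10 per treatment group".

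The order of events is also given. In section 9 eligibility is assessed after consent ("Once the participant has signed the informed consent, complete medical history, inclusion/exclusion criteria"). In section 6.6 those who meet the criteria and "who remain interested in participating in the 2 week intervention will be randomized to treatment or sham groups". Screen failures therefore come out of the consented number before anyone is randomised.

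**The concern.** The margin between 206 consents and 150 participants is 56. The screen-failure allowance alone can use 50 of it. What is left is far smaller than a 20% loss, yet the sentence says that the figure allows for both.

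The protocol text does not say whether the 35, 10, 10 and 20 per arm are numbers randomised or numbers expected to finish. A reader who takes the attrition clause at face value will expect those sizes at the post-intervention visit. The protocol's own allowances give about 28, 8, 8 and 16 per arm, or 29, 8, 8 and 17 if all 156 are randomised. The groups are analysed separately (section 7.3), so the loss falls on cells that are already small. Nor can the study team tell from the text whether enrolment should stop at 150 randomised or go on to about 188.

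**Working it through.** **Inputs (section 6.2).** Target 70 + 20 + 20 + 40 = 150. Attrition 20%. Screen failures at most 50. Planned consents 206.

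**Trying to reproduce 206.** These are the usual ways to combine the inputs:

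| Calculation | Consents |
|---|---|
| 150/0.8 = 187.5, rounded up to 188; + 50 | 238 |
| 150 × 1.2 + 50 | 230 |
| (150 + 50)/0.8 | 250 |
| (150 + 50) × 1.2 | 240 |
| Each arm divided by 0.8 and rounded up, + 50 | 240 |
| Attrition only, 150/0.8 or 150 × 1.2 | 188 or 180 |
| Screen failures only, 150 + 50 | 200 |

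None that uses all three inputs gives 206. The nearest, 200, contains no attrition allowance. As it happens, 130 × 1.2 + 50 = 206, and 130 is the total without one MCI group of 20. The figure could be left over from a smaller target, but that is a guess which the protocol does not confirm, and nothing below depends on it.

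**What 206 consents yield.** Completers = (206 − failures) × 0.8:

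| Screen failures | Randomised | Completers |
|---|---|---|
| 50 | 156 | 124.8 |
| 40 | 166 | 132.8 |
| 30 | 176 | 140.8 |
| 19 | 187 | 149.6 |
| 18 | 188 | 150.4 |

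With 50 failures, 150 completers would require attrition of no more than 1 − 150/156 = 6/156 = 3.8%.

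**If the 150 are randomised.** Consents needed: 150 + 50 = 200. Spare places: 206 − 200 = 6, which is 6/150 = 4%, against expected losses of 150 × 0.2 = 30. Expected completers: 150 × 0.8 = 120, or 35/10/10/20 × 0.8 = 28/8/8/16 per arm. No replacement of dropouts is described, so losses after randomisation call for no further consents.

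**If the 150 are completers.** Randomised: 150/0.8 = 187.5, so 188. Consents: 188 + 50 = 238, and 238 − 206 = 32 more than planned. With whole numbers per arm, 43.75, 12.5, 12.5 and 25 become 44, 13, 13 and 25. Then 2 × 95 = 190 are randomised and 240 consented, 34 more than planned.

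**If 206 is kept on the completing reading.** Per arm, 35/10/10/20 × (156/150) × 0.8 = 29.1/8.3/8.3/16.6, assuming that losses are spread in proportion to group size.

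**The case against.** The strongest reply is that the protocol never promises 150 completers. The per-arm sizes appear under 1:1 assignment, which suggests that they are randomised numbers, and on that reading 206 exceeds the 200 needed. This largely stands: enrolment is then sufficient, and what is wrong is the stated reason for the figure. It does not rescue the reason, because the sentence expressly includes attrition and 6 places are not a 20% allowance.

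A second reply is that 50 is an upper limit, so the shortfall in completers is a worst case. That is correct, and the table shows how it shrinks. Still, a figure said to account for these allowances should hold when they are used in full.

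A third is that some attrition may come between eligibility and randomisation, since only those still interested are randomised and section 6.2 does not say when attrition starts. Such losses would use extra consents, so the spare places would have a purpose. But if the whole 20% fell there, 156 × 0.8, about 125, would be randomised, which is again short of 150. The point does show that the base for the 20% needs defining.

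Finally, the design diagram announced at the end of section 6.1 is not in the text available here, and it may show which reading is meant. The arithmetic fails on both readings, so the diagram could settle only which correction applies.

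**Conclusion.** The concern holds. At the protocol's full allowances, 206 consents give about 125 completers, roughly 25 fewer than 150. If the 150 are randomised, 206 is adequate for randomising them, but the statement that it covers attrition is wrong: 4% is available against 20% stated. Sections 6.1 and 7.2.a favour the randomised reading. Only the attrition clause in section 6.2 points the other way.

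The completer figures assume 50 screen failures and that the 20% applies to those randomised. The shortfall against 150 completers disappears at 18 or fewer failures.

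The practical effect is modest. Section 6.7.2 presents the study as a means of gauging effect sizes and feasibility, and no power claim depends on these counts. Completers are not necessarily the analysed sample either: under section 7.2.b the first analysis set includes anyone with at least one week of intervention. This should be corrected, but it does not threaten the design.

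**What to change.** In sections 6.2 and 7.2.a, state whether 35, 10, 10 and 20 per arm are randomised or completing participants, say what the 20% attrition applies to, and restate the consent figure to match.

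- **Randomised.** Give 150 plus up to 50, so up to 200 consents; 206 may stay as a ceiling with 6 spare places. Remove the claim that the figure covers attrition, and state that about 120 are expected to complete (28, 8, 8 and 16 per arm). Cost: one corrected sentence in 6.2 and one clarifying word in 6.2 and 7.2.a, with no added participants.
- **Completing.** Give 188 randomised and up to 238 consents, or 190 and 240 with whole numbers per arm. Cost: up to 32 or 34 consents beyond 206.
- **Completing, with consents held at 206.** Lower the stated completers to about 125 (about 29, 8, 8 and 17 per arm if losses are proportional). Cost: rewritten group sizes in both sections.
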